## **10.3 Methods and Timing for Capturing and Assessing Safety Parameters**

### **10.3.1 Adverse Event Reporting Period**

The study AE reporting period is as follows:

- After informed consent but prior to initiation of study drug, only SAEs associated with any protocol-imposed interventions will be collected; AEs occurring during this time period should be recorded on the Medical History eCRF.
- After informed consent is obtained and following infusion of study drug, the reporting period for all non-serious AEs and SAEs begins and continues for approximately 5 years or until study discontinuation/termination, whichever is longer.

The criteria for determining, and the reporting of SAEs is provided in Section 10.2.

### **10.3.2 Eliciting Adverse Events**

Care will be taken not to introduce bias when detecting AEs and/or SAEs. Open-ended and non-leading verbal questioning of the subject is the preferred method to inquire about AE occurrences. The Investigator will record all relevant AE/SAE/EOSI information in the subject's medical record and AE Case Report Form (eCRF).

### **10.3.3 Assessment of Seriousness, Severity, and Causality**

The Investigator responsible for the care of the subject or medically qualified designee will assess AEs for severity, relationship to study drug, and seriousness (refer to Section 10.2 for SAE definitions). These assessments must be made by a study clinician with the training and

authority to make a diagnosis (eg, MD/DO, physician's assistant, nurse practitioner, or DDS).

#### **10.3.3.1 Seriousness**

The Investigator will assess if an AE should be classified as “serious” based on the seriousness criteria enumerated in Section 10.2. Seriousness serves as a guide for defining regulatory reporting obligations.

#### **10.3.3.2 Severity**

Severity (as in mild, moderate, or severe headache) is not equivalent to seriousness, which is based on subject/event outcome or action criteria usually associated with events that pose a threat to a subject's life or functioning. The Investigator will determine the severity of each AE, SAE and EOSI using the NCI CTCAE v4.03. Adverse events that do not have a corresponding CTCAE term will be assessed according to the general guidelines for grading used in the CTCAE v4.03 as stated in [Table 10.3.3.2.1](#).

**Table 10.3.3.2.1: Adverse Event Grading (Severity) Scale**

Grade	Description	
1	Mild: asymptomatic or mild symptoms; clinical or diagnostic observations only; intervention not indicated	
2	Moderate: minimal, local or noninvasive intervention indicated; limiting age-appropriate instrumental activities of daily living (ADL) a	
3	Severe or medically significant but not immediately life-threatening: hospitalization or prolongation of hospitalization indicated; disabling; limiting self-care ADL b	
4	Life threatening consequences; urgent intervention indicated	Grade 4 and 5 AEs should always be reported as SAEs
5	Death related to AE	

a Instrumental ADL refer to the following examples: preparing meals, shopping for groceries or clothes, using the telephone, managing money.

b Self-care ADL refer to the following examples: bathing, dressing and undressing, feeding oneself, using the toilet, taking medications, not bedridden.

#### **10.3.3.3 Causality**

The Investigator will determine the relationship of an AE to the study drug and will record it on the source documents and AE eCRF. To ensure consistency of causality assessments, Investigators should apply the guidance in [Table 10.3.3.1](#).

**Table 10.3.3.3.1: Causality Attribution Guidance**

Relationship	Description
Not Related	
 
Exposure to the IP has not occurred
 
 
OR
 
 
The administration of the IP and the occurrence of the AE are not reasonably related in time
 
 
OR
 
 
The AE is considered likely to be related to an etiology other than the use of the IP; that is, there are no facts, evidence, or arguments to suggest a causal relationship to the IP.
 

Related	
 
The administration of the IP and the occurrence of the AE are reasonably related in time
 
 
AND
 
 
The AE could possibly be explained by factors or causes other than exposure to the IP
 
 
OR
 
 
The administration of IP and the occurrence of the AE are reasonably related in time
 
 
AND
 
 
The AE is more likely explained by exposure to the IP than by other factors or causes.
 

Factors suggestive of a causal relationship could include (but are not limited to):

- Plausible temporal relationship
- Absence of alternative explanations
- Rarity of event in a given patient or disease state
- Absence of event prior to study drug exposure
- Consistency with study product pharmacology
- Known relationship to underlying mechanism of study drug action
- Similarity to adverse reactions seen with related drug products
- Abatement of AE with discontinuation of study drug, and/or recurrence of AE with reintroduction of study drug

The Investigator's assessment of causality for individual AE reports is part of the study documentation process. Regardless of the Investigator's assessment of causality for

---

individual AE reports, the Sponsor will promptly evaluate all reported SAEs against cumulative product experience to identify and expeditiously communicate possible new safety findings to Investigators and applicable regulatory authorities.

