### **9.3.3.1 Study Safety Evaluation Criteria**

If any of the following events occur in a subject in the study who has received BMN 270 infusion, an urgent evaluation by the DMC will be required and further enrollment into the trial will be temporarily put on hold if recommended by the DMC per Section 9.1.

1. Liver dysfunction (criteria do not apply to ALT elevations with an extra-hepatic etiology):
  - o ALT > 5x ULN, for more than 2 weeks
  - o ALT > 3x ULN **and** (total bilirubin >2x ULN **or** INR >1.5)
  - o ALT > 3x ULN with signs and symptoms of liver dysfunction
2. The occurrence of Grade 4 or Grade 5 adverse events assessed as related to study drug (events of liver dysfunction are defined above).
3. The occurrence of an AE of hepatic failure.
4. The detection of high-titer neutralizing antibodies (>5 BU) to hFVIII following BMN 270 infusion in two subjects.
5. The occurrence of any cancer (except non-melanoma skin cancer) at any point after BMN 270 infusion.
6. The occurrence of a thromboembolic event with FVIII activity > 150 IU/dL in one subject.

If any of the following events occurs in a subject in the study who has received BMN 270 infusion, an urgent evaluation by the DMC will be required. Further enrollment into the trial will continue while DMC evaluation is ongoing, unless deemed otherwise by the DMC:

1. The detection of high-titer neutralizing antibodies (>5 BU) to hFVIII following BMN 270 infusion in one subject.
2. Occurrence of a thromboembolic event in one subject.

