14.1.2 Drug-Related Adverse Events

All TEAEs assessed by investigator as investigational product related (i.e., ADRs) will be included in a listing.

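### The causality table lets a missing time link to the single infusion alone make an adverse event Not Related, and its first Related arm never asks whether the product could be a cause

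*Protocol*

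**What the plan says.** Protocol Section 10.3.3.3 directs investigators to Table 10.3.3.3.1 so that causality is judged consistently. The table has two categories.

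- **Not Related** has three limbs joined by OR. The first is that no exposure occurred. The second is that "The administration of the IP and the occurrence of the AE are not reasonably related in time". The third is that "The AE is considered likely to be related to an etiology other than the use of the IP", explained by a clause saying that "there are no facts, evidence, or arguments to suggest a causal relationship to the IP".
- **Related** has two arms joined by OR, and both require that timing be reasonable ("The administration of the IP and the occurrence of the AE are reasonably related in time"). The first arm adds that "The AE could possibly be explained by factors or causes other than exposure to the IP". The second adds that "The AE is more likely explained by exposure to the IP than by other factors or causes".

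A non-exhaustive list of factors suggesting causality follows. It includes plausible timing, consistency with the product's pharmacology, a known mechanism, and abatement or recurrence when the drug is stopped or reintroduced.

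The relatedness label is used in three places:

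- SAP 14.1 defines an ADR by a reasonable possibility that the product caused the event, then counts as ADRs the events that the investigator calls related under the protocol guidance. SAP 14.1.2 follows: "All TEAEs assessed by investigator as investigational product related (i.e., ADRs) will be included in a listing". SAP 14.1.3 does the same for serious ADRs.
- Protocol Section 9.3.3.1 makes one urgent DMC evaluation depend on it: "The occurrence of Grade 4 or Grade 5 adverse events assessed as related to study drug".
- Protocol Section 10.5.1 has suspected unexpected reactions (SUSARs) reported to authorities on expedited timelines.

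Protocol Section 7.3 describes a single dose designed for expression that may last for life. Section 10.3.1 sets adverse event collection at about 5 years.

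**The concern.** The timing test is written against the act of administration. That works for a drug given repeatedly, where a late event usually has a recent dose behind it. Here there is one infusion, and the biological exposure (vector and transgene product) is meant to continue. An effect of continuing expression may appear long after Day 1. If an investigator reads the time link as time since infusion, the table closes the question there, even when pharmacology or mechanism points to the product.

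The first Related arm has a separate fault. It pairs reasonable timing with the possibility of some *other* cause and never asks whether the product itself could be one. The protocol rule therefore does not carry out the SAP definition that relies on it. Read literally, a well-timed event with a likely alternative cause can also satisfy the third Not Related limb, and no rule says which label prevails.

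At stake is the consistency of the ADR and serious-ADR listings, of the investigator's contribution to SUSAR assessment, and of the related Grade 4 or 5 criterion for the DMC.

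**Working it through.** The plan gives no figure to reproduce, because the point concerns the logic of a table. The check had two parts.

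**1. Truth table for an exposed subject.** The inputs are the table's own conditions:

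- T: reasonably related in time (yes or no).
- Alternative cause (four levels): none possible; possible but product more likely; balanced; other cause likely.
- Evidence for the product (yes or no).

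This gives 2 × 4 × 2 = 16 cases, 8 with reasonable timing and 8 without. The rules are:

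- Not Related = (not T) OR limb 3.
- Related = (T AND another cause possible) OR (T AND product more likely).

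Limb 3 can be read three ways: (A) another etiology is likely; (B) as A, and there is no evidence for the product; (C) as B, with reasonable timing itself counted as evidence for the product.

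| Result | Reading A | Reading B | Reading C |
|---|---|---|---|
| Not reasonably timed: Not Related | 8 of 8 | 8 of 8 | 8 of 8 |
| Reasonably timed: Related only | 6 of 8 | 7 of 8 | 8 of 8 |
| Reasonably timed: meets both | 2 of 8 | 1 of 8 | 0 of 8 |

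No case meets neither definition. The timing result is the same under every reading. Of the 8 untimely cases, 4 have evidence for the product, and in 2 of those 4 the product is the likelier cause. All are still Not Related, because limb 2 stands alone and both Related arms need T. The listed factors on pharmacology and mechanism cannot override limb 2 as written.

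The overlap does depend on the reading. It disappears only under C, which the table does not state, although it lists plausible timing among the factors suggesting causality.

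**2. Where the label acts.** Protocol Section 9.3.3.1 has 6 criteria that can lead to an enrollment hold and 2 that call for urgent evaluation while enrollment continues, so 6 + 2 = 8.

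- Using study-drug relatedness: 1 of 8 (Grade 4 or 5 events).
- Not using it: 7 of 8 (liver dysfunction; hepatic failure; antibodies above 5 BU in two subjects; any cancer at any time; thromboembolism with FVIII above 150 IU/dL; antibodies above 5 BU in one subject; any thromboembolic event). The liver criteria do exclude ALT elevations of extra-hepatic origin, which is a different judgment.

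In the SAP, the listings of all adverse events (14.1.1), of deaths and all SAEs (14.1.3) and of events of special interest (14.1.5) carry no relatedness filter. The ADR listing and the serious-ADR part of 14.1.3 do.

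**The case against.** The best case for leaving the table alone has several parts.

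*No time limit is set.* A reader might infer that events in Years 2 to 5 are automatically Not Related, and note that 208 of the 52 + 208 = 260 follow-up weeks lie beyond Week 52. The documents do not say this. Reasonable timing is left to judgment, and an investigator who knows expression may persist can accept a Year 3 event. Protocol Section 10.7 expects possibly related events to be notified even after the study. This stands: the table permits exclusion on time alone but does not require it for late events. Its weakness is that it gives no direction in a passage meant to secure consistency.

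*The overlap depends on reading.* The clause "there are no facts, evidence, or arguments to suggest a causal relationship to the IP" narrows the third limb, and on the strictest reading the overlap is nil. A reader might also infer that confounded events are forced out of the ADR listing. They are not, since a well-timed confounded event meets the first Related arm. What remains is ambiguity without a tie-break.

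*Events are not lost.* A reader might infer that mislabelled events vanish or bypass the DMC. They do not:

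- The text below the table has the sponsor evaluate every reported SAE, whatever the investigator's causality call.
- Grade 4 and 5 events are always SAEs (Table 10.3.3.2.1), and SAEs are reported within 24 hours related or not (Section 10.5.1). That section also makes the sponsor responsible for identifying SUSARs.
- Events of special interest are reported irrespective of causality (Section 10.2.1).
- The DMC reviews individual safety data continuously (Section 15).

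This largely stands. The gap is a late event that is neither serious nor of special interest: no second causality review is stated for it.

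*The stopping and reintroduction factor.* It may look meaningless after one infusion, but Section 9.4.4 allows a halted infusion to be restarted, so abatement and recurrence can be observed.

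**Conclusion.** The point holds as a drafting fault with limited reach. On the text, absence of a reasonable time link to administration is sufficient for Not Related and its presence is necessary for Related (8 of 8 untimely cases under every reading). That does not fit a one-time vector with persisting expression. The first Related arm does not test product causation and so does not match the SAP definition of an ADR. The overlap is real on a literal reading (2 or 1 of 8 well-timed cases) but not on the strictest (0 of 8).

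These counts describe the rule, not the expected number of mislabelled events, which the documents do not allow one to estimate. The conclusion assumes that some investigators would read the time link as time since infusion; the table neither says so nor excludes it.

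The practical effect here is small. SAP Sections 1 and 4 state that one subject was enrolled and enrollment has ended, so an enrollment hold no longer matters and the ADR listing is a subset of one subject's events. The label keeps some weight because the listings support a marketing application and, with one subject, would be read event by event.

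**What to change.** Amend Table 10.3.3.3.1 in three respects:

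1. State that timing is judged against exposure to the product, including persisting vector or transgene expression, so that time since infusion alone does not make an event Not Related.
2. Reword the second condition of the first Related arm along these lines: *could possibly be explained by exposure to the IP, although other factors may also explain it*. This brings the rule into line with SAP 14.1.
3. Limit the third Not Related limb to events with no reasonable possibility of product causation, and name Related as the default when both categories could apply. The categories are then mutually exclusive.

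Keep the factor on abatement and recurrence. The SAP needs no change, since it defers to the protocol guidance.

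The cost is one table in the next amendment and a note to sites. With one enrolled subject, checking labels already assigned is a small task. The downside is that more late events will be classed as related: once persisting expression counts as exposure, few events in the 5 years would fail on timing, and the decision rests on whether product causation is reasonably possible. The documents give no basis for estimating how many labels would change.

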## **10.4 Procedures for Recording Adverse Events**

### **10.4.1 Recording Adverse Events on a eCRF**

Investigators should use precise medical terminology when recording AEs or SAEs on the AE eCRF. Avoid colloquialisms and abbreviations.

Record only one diagnosis, sign, or symptom per event field on the AE eCRF (eg, nausea and vomiting should not be recorded in the same entry, but as 2 separate entries).

In order to classify AEs and diseases, preferred terms will be assigned by the Sponsor to the original terms entered on the AE eCRF, using MedDRA (Medical Dictionary for Regulatory Activities) terminology.

#### **10.4.1.1 Diagnosis versus Signs and Symptoms**

The Investigator will attempt to establish a diagnosis of the event based on signs, symptoms, and/or other clinical information. Whenever possible, the diagnosis (not the individual signs/symptoms) will be documented as the AE/SAE. Using accepted medical terminology, enter the diagnosis (if known). If not known, enter sign(s) and/or symptom(s). If a diagnosis subsequently becomes available, then this diagnosis should be entered on the AE (or SAE, as appropriate) eCRF, replacing the original entries where appropriate.

#### **10.4.1.2 Adverse Events Occurring Secondary to Other Events**

In general, AEs occurring secondary to other events (eg, cascade events) should be identified by their primary cause. For example, if severe diarrhea is known to have resulted in dehydration, it is sufficient to record only diarrhea as an AE or SAE on the AE eCRF.

However, medically important events that may be linked and/or separated in time should be recorded as independent events on the AE eCRF. For example, if severe hemorrhage leads to renal failure, both events should be recorded separately on the AE eCRF.

#### **10.4.1.3 Persistent or Recurrent Adverse Events**

A persistent AE (duration of adverse event > 7 days) is one that extends continuously, without resolution, between subject evaluation time points. Events that change in severity necessitate the recording of an additional AE. AEs that do not have a change in severity should be recorded only once on the eCRF.

A recurrent AE is one that occurs and resolves between subject evaluation time points, but then subsequently recurs. All recurrences of the AE should be recorded on the AE eCRF. For example, if a subject has an adverse event of ALT increased that subsequently resolves, but the subject's ALT increases again, that should be reported as two adverse events – the initial ALT increase, and the second ALT increase.

#### **10.4.1.4 Abnormal Laboratory Values**

Laboratory test results will be recorded on the laboratory results pages of the eCRF, or appear on electronically produced laboratory reports submitted directly from the central laboratory, if applicable.

Any laboratory result abnormality fulfilling the criteria for a SAE or EOSI should be reported as such, and recorded in the AE eCRF.

Any laboratory result abnormality of CTCAE Grade 4 or 5 should be recorded as an SAE in the AE eCRF.

A clinical laboratory abnormality is considered clinically significant and should be documented as an AE if not refuted by a repeat test to confirm the abnormality and **any** one or more of the following conditions is met:

- Accompanied by clinical symptoms
- Requiring a change in concomitant therapy (eg, addition of, interruption of, discontinuation of, or any other change in a concomitant medication, therapy or treatment).
- The abnormality suggests a disease and/or organ toxicity
- The abnormality is of a degree that requires active management (eg, change of dose, discontinuation of study drug, more frequent follow-up assessments, further diagnostic investigation, etc.)

**This applies to** any protocol and non-protocol specified safety and efficacy laboratory result from tests performed after the first dose of study medication that falls outside the laboratory reference range and meets the clinical significance criteria.

**This does not apply to** any abnormal laboratory result that falls outside the laboratory reference range but that does not meet the clinical significance criteria (these will be analyzed and reported as laboratory abnormalities), those that are considered AEs of the type explicitly exempted by the protocol, or those which are a result of an AE that has already been reported.

---

For purposes of this study, laboratory tests showing a decreased level of FVIII activity should not be reported as adverse events unless there is an impact to clinical outcomes (eg, increased rate of bleeding, worsening of joint disease).

#### **10.4.1.5 Pre-existing Conditions**

A pre-existing condition is one that is present prior to administration of BMN 270. Such conditions should be recorded as medical history on the appropriate eCRF.

A pre-existing condition should be recorded as an AE or SAE during the study **only** if the frequency, intensity, or character of the condition worsens during the study period. It is important to convey the concept that a pre-existing condition has changed by including applicable language in the verbatim description of the event (eg, *more frequent* headaches).

#### **10.4.1.6 General Physical Examination Findings**

At screening, any clinically significant abnormality should be recorded as a pre-existing condition (refer to Section 10.4.1.5). During the study, any new clinically significant findings and/or abnormalities discovered on physical examination that meet the definition of an AE (or an SAE) must be recorded and documented as an AE or SAE on the AE eCRF.

#### **10.4.1.7 Hospitalization, Prolonged Hospitalization, or Surgery**

Any AE that results in hospitalization or prolonged hospitalization should be documented and reported as an SAE unless specifically instructed otherwise in this protocol (refer to Section 10.2).

There are some hospitalization scenarios that do not require reporting as an SAE when there is no occurrence of an AE. These scenarios include planned hospitalizations or prolonged hospitalizations to:

- Perform a protocol-mandated efficacy measurement
- Undergo a diagnostic or elective surgical procedure for a pre-existing medical condition that has not worsened
- Insert an in-dwelling IV catheter (such as a Port-a-Cath or other brand, if applicable) for administration of study drug or FVIII replacement therapy
- Receive scheduled therapy (study drug or otherwise) for the study indication

#### **10.4.1.8 Deaths**

All deaths that occur during the AE reporting period (refer to Section 10.3.1), regardless of attribution, will be recorded on the AE eCRF and expeditiously reported to the Sponsor as an SAE.

---

When recording a death, the event or condition that caused or contributed to the fatal outcome should be recorded as the single medical concept on the eCRF. If the cause of death is unknown and cannot be ascertained at the time of reporting, record “Unexplained Death” or “Death of Unknown Cause” on the AE eCRF.

